#### Investigation of hysteresis:

If a QTc effect ( $\Delta\Delta QTcF$ ) exceeding 10 msec cannot be excluded in the by-timepoint analysis of the two highest dose groups, hysteresis, *i.e.*, difference in peak QT response and  $C_{max}$ , will be explored through visual inspection of overlaid PK and  $\Delta\Delta QTc$  time curves and through so called hysteresis loops for each dose of Modufolin® for Injection, 100 mg

#### Appropriateness of a linear model:

To assess the appropriateness of a linear model, normal QQ-plots for the residuals and plots of weighted residuals vs. concentration and vs. fitted values will be produced. The scatter plot of residuals vs concentration by Loess (*i.e.*, locally weighted scatterplot smoothing as described in the publication by Cleveland) fitting will be also produced with an optimal smoothing parameter selected by the Akaike information criterion with a correction (AICC). In addition, a model with a quadratic term in concentration will be fitted and the quadratic term will be tested on the two-sided 5% level. If there is an indication that a linear model is inappropriate, additional models will be fitted, in particular:

- An E-max model;
- A log-linear model where the plasma concentration C is replaced by  $\log(C/C_0)$ ,  $C_0$  is the limit of quantification of the assay used to determine C and all values below  $C_0$  are replaced by  $C_0$  (*i.e.*,  $\log[C_0/C_0] = 0$ ).

The Exposure-Response analysis will then be repeated for the model found to best accommodate the nonlinearity detected.

#### 17.4.4 By-time point analysis:

The analysis for QTcF will be based on a linear mixed-effects model with change-from-baseline QTcF ( $\Delta QTcF$ ) as the dependent variable, time (categorical), treatment (Modufolin® for Injection, 100 mg and placebo), and time-by-treatment interaction as fixed effects, and baseline QTcF as a covariate. Subject will be included as a random effect for the intercept. Subject dosed with placebo will be analyzed as a pooled group. An unstructured covariance

matrix will be specified for the repeated measures at post-dose time points for each subject. If the model with unstructured covariance matrix fails to converge, other covariance matrix such as autoregressive and compound symmetry will be considered. From this analysis, the least-squares (LS) mean and 2-sided 90 % CIs will be calculated for the contrast “Modufolin® versus placebo” at each dose of Modufolin® and each post-dose time point, separately.

For HR, PR, and QRS intervals, the analysis will be based on the change-from-baseline values ( $\Delta$ HR,  $\Delta$ PR,  $\Delta$ QRS). The same model will be used as described for QTcF. The LS mean, SE and 90% CI from the statistical modeling for both change-from-baseline and placebo-corrected change-from-baseline values will be listed in the tables and graphically displayed.

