#### *By-Time point Analysis*

The analysis for QTcF will be based on a linear mixed-effects model with change-from-baseline QTcF ( $\Delta QTcF$ ) as the dependent variable, time (categorical), treatment (Modufolin® for Injection, 100 mg and placebo), and time-by-treatment interaction as fixed effects, and baseline QTcF as a covariate. Subject will be included as a random effect for the intercept. Subject dosed with placebo will be analyzed as a pooled group. An unstructured covariance matrix will be specified for the repeated measures at post-dose time points for each subject. If the model with unstructured covariance matrix fails to converge, other covariance matrix such as autoregressive and compound symmetry will be considered. From this analysis, the least-squares (LS) mean and 2-sided 90% CIs will be calculated for the contrast “Modufolin® versus placebo” at each dose of Modufolin® for Injection, 100 mg and each post-dose time point, separately.

For HR, PR, and QRS intervals, the analysis will be based on the change-from-baseline values ( $\Delta HR$ ,  $\Delta PR$ ,  $\Delta QRS$ ). The same model will be used as described for QTcF. The LS mean, SE and 90% CI from the statistical modeling for both change-from-baseline and placebo-corrected change-from-baseline values will be listed in the tables and graphically displayed.

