#### 8.2.1 Secondary endpoints

The secondary evaluation parameters are:

- Change-from-baseline heart rate, PR and QRS interval ( $\Delta$ HR,  $\Delta$ PR and  $\Delta$ QRS)
- Categorical outliers for QTcF, HR, PR interval, QRS interval;
- Categorical analysis for T wave morphology;
- Relationship between Modufolin® plasma concentration and  $\Delta\Delta$ QTc
- Frequency, seriousness and intensity of AEs
- Physical examination
- Vital signs
- Safety laboratory measurements
- Plasma PK characteristics of Modufolin® for Injection, 100 mg and its metabolites:
  - [6R]-5,10- Methylene Tetrahydrofolate (MTHF; Modufolin® for Injection, 100 mg)
  - [6S]-5-Methyl-Tetrahydrofolate (5-Methyl-THF)
  - [6S]-Tetrahydrofolate (THF)
  - [6S]-5-Formyl-Tetrahydrofolic acid (5-Formyl-THF)

The PK parameters to be evaluated are listed in Section [17.7.5](#).

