### 12.3.3 High-precision QT analysis

High-precision QT analysis will be performed on all analyzable (non-artifact) beats in the 10 ECG replicates. Statistical quality control procedures are used to review and assess all beats and identify "high" and "low" confidence beats using several criteria, including:

- QT or QTc values exceeding or below certain thresholds (biologically unlikely).
- RR values exceeding or below certain thresholds (biologically unlikely).
- Rapid changes in QT, QTc or RR from beat to beat.

Measurements of all primary ECG parameters (QT, QTc, RR) in all recorded beats of all replicates that are deemed “high confidence” is performed using COMPAS software. All low confidence beats are reviewed manually and adjudicated using pass-fail criteria. The final QC assessment is performed by a cardiologist. The beats found acceptable by manual review are included in the analysis. The median QT, QTc, and RR value from each extracted replicate is calculated, and then the mean of all available medians from a nominal time point is used as the subject’s reportable value at that time point.

Categorical T-wave morphology analysis and the measurement of PR and QRS intervals will be performed manually in 3 of the 10 ECG replicates at each time point ([Table 5](#)). Each fiducial point (onset of P-wave, onset of Q-wave, offset of S-wave, and offset of T-wave) is electronically marked.

In addition to the T-wave categorical analysis, the presence of abnormal U-waves is noted.

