## 17.4 Electrocardiogram analysis

### 17.4.1 Baseline

For all ECG parameters, baseline is defined as the average of the measured QTc intervals from the 3 pre-dose time points (45, 30, and 15 min pre-dose) on Day 1.

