#### 17.4.5 Categorical analyses

The analysis results for categorical outliers, and T-wave morphology will be summarized in frequency tables with counts percentages for both number of subjects and number of time points. For categorical outliers, the number (percentage) of subjects as well as time points who had increases in absolute QTcF values  $>450$  and  $\leq 480$  msec,  $>480$  and  $\leq 500$  msec, and 500 msec, and changes from pre-dose baseline of  $>30$  and  $\leq 60$  msec, and  $>60$  msec; increase in PR from pre-dose baseline  $>25\%$  to a PR  $>200$  msec; increase in QRS from pre-dose baseline  $>25\%$  to a QRS  $>120$  msec; decrease in HR from pre-dose baseline  $>25\%$  to a HR  $<50$  bpm; and increase in HR from pre-dose baseline  $>25\%$  to a HR  $>100$  bpm will be determined. For T-wave morphology, the analyses will be focused on change from baseline (*i.e.*, treatment-emergent changes).

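### The ECG baseline is defined as a QTc average even for HR, PR and QRS, and their models inherit baseline QTcF as covariate; secondarily, the random intercept in the by-time-point model is redundant

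*Protocol*

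**What the plan says.** **Baseline.** Section 17.4.1 gives the protocol's only definition of baseline for the ECG analysis: "For all ECG parameters, baseline is defined as the average of the measured QTc intervals from the 3 pre-dose time points". Those times fall 15, 30 and 45 min before dosing. Section 17.4.4 fits change in QTcF with baseline QTcF as covariate. For change in HR, PR and QRS it adds: "The same model will be used as described for QTcF". The synopsis repeats this by-time-point paragraph.

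Two other sections need a baseline specific to each parameter. Section 8.2.1 lists as secondary endpoints "Change-from-baseline heart rate, PR and QRS interval". Section 17.4.5 defines outliers by percentage change in the parameter itself, for example "increase in PR from pre-dose baseline" of more than 25% to a value above 200 msec.

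**Covariance.** In the same model, "Subject will be included as a random effect for the intercept". Both the synopsis and 17.4.4 add: "An unstructured covariance matrix will be specified for the repeated measures at post-dose time points for each subject". The fallback reads: "If the model with unstructured covariance matrix fails to converge, other covariance matrix such as autoregressive and compound symmetry will be considered". Nothing says that the random intercept is dropped at any step.

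**The concern.** A QTc interval cannot serve as the baseline of a heart rate, a PR interval or a QRS duration. If 17.4.1 is followed, the change scores for three secondary endpoints and their outlier categories lose their meaning.

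The covariate is the less visible half. A programmer would probably notice a change in heart rate of several hundred. A model for change in PR that adjusts for baseline QTcF would run without any warning.

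The covariance wording raises a smaller issue. A random intercept adds one constant to every element of the within-subject covariance matrix, and an unstructured matrix already allows any such shift. The model therefore carries a parameter that the data cannot determine, while the plan makes failure to converge the trigger for changing the covariance structure. The trigger could then respond to how the software treats a singular matrix and not to the data. The by-time-point model also decides, in 17.4.3, whether hysteresis is explored.

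**Working it through.** **1. The plan's own figure.** Inputs from 17.2: SD 7 msec, one-sided 0.05, 24 active and 9 placebo, margin 10 msec, true effect 3 msec.
- SE = 7 × √(1/24 + 1/9) = 2.736 msec.
- (10 − 3)/2.736 − 1.645 = 0.913, so power is 81.95%, against 82% stated.
- For 48 and 18 subjects the same formula gives 97.58%, against 97.5% stated.

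Both figures reproduce, and neither uses the baseline rule or the by-time-point model.

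**2. Outlier rules under the literal baseline.** The thresholds come from 17.4.5. For the QTc baseline I take 350 to 450 msec: 450 is the screening limit in 10.5, and 350 is an assumption.
- A rise of more than 25% needs a value above 1.25 × 350 = 437.5 up to 1.25 × 450 = 562.5. For PR and QRS that is in msec, for HR in bpm. These three categories would be empty in practice.
- A fall in HR of more than 25% needs a value below 0.75 × 350 = 262.5 or more. Every heart rate meets that, so the rule shrinks to HR below 50 bpm. Section 10.5 admits subjects with a pulse down to 40, so a subject at 45 bpm throughout would count as an outlier without any change.

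**3. Change scores under the literal baseline**, evaluated at the protocol's own thresholds.
- PR of 200 msec: 200 − 350 = −150, to 200 − 450 = −250.
- QRS of 120 msec: −230 to −330.
- HR of 50 bpm: −300 to −400, in mixed units.

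**4. Are proper baselines available?** Yes. Section 12.3.3 says that "the measurement of PR and QRS intervals will be performed manually in 3 of the 10 ECG replicates at each time point", and RR, from which HR follows, is measured there too. The three pre-dose extractions are in Table 1.

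**5. Identifiability.** Table 1 has 12 post-dose times (5, 15, 30 min; 1, 2, 3, 4, 5, 6, 8, 12, 24 h). The marginal covariance is V = σ_b²·J + R, where J is the all-ones matrix. Counting parameters against the rank of the map into V:

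| R | Parameters with intercept | Rank |
|---|---|---|
| Unstructured | 12 × 13/2 + 1 = 79 | 78 |
| Compound symmetry | 3 | 2 |
| AR(1) | 3 | 3 |

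For compound symmetry, R = σ²·I + c·J, so only the sum c + σ_b² enters V. The redundancy with these two structures holds for any number of times from two upwards.

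**6. What stays the same.** In one simulated data set of 33 subjects, intercept variances of 0, 5, 15 and 25 with a compensating unstructured R all gave REML log-likelihood −751.131, contrast −1.769 and SE 3.064. Three compound-symmetry splits likewise all gave −762.604 and SE 3.436.

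**7. What may depend on the software.** I used 200 simulated trials with groups of 9/8/8/8, SD 7 msec, complete data and correlation 0.4 + 0.6 × 0.5^lag (an assumption).
- Scoring with an ordinary inverse converged in 200/200 for unstructured alone. With the intercept added it met a singular information matrix in 200/200, as the rank deficit requires.
- A generalised inverse converged in 200/200 with the same SDs.
- A quasi-Newton optimiser also converged in 200/200 with the intercept included.

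**The case against.** **On the baseline.** The sentence in 17.4.1 is very likely a drafting slip, and the context shows what was meant. Subtracting milliseconds from beats per minute makes no sense, and carrying over the same model can be read as the same structure with each parameter's own baseline. That is a fair guess at intent, and the figures in steps 2 and 3 describe an analysis that few would knowingly run. But 17.4.1 expressly covers all ECG parameters, no other ECG analysis baseline is given, and the only covariate named is baseline QTcF. This is a stated rule, not a detail left to the SAP. A SAP would have to inherit it or contradict it.

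**On the covariance.** The reply is stronger here. A likelihood that is flat in one direction still has a maximum, and step 7 shows that common algorithms reach it. SAS 9.4, the software named in 17.1, was not tested. What stands is that a redundant parameter sits beside a convergence trigger, and that one of the two named fallbacks repeats the redundancy.

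**Stronger readings that the protocol does not support.**
- A reader might infer that the model's variance as a whole is unidentifiable, or that the by-time-point estimates are wrong. Only the split between intercept variance and residual covariance is undetermined.
- A reader might try to put a figure on interval widths after a fallback, or on precision lost through the wrong covariate. Both need SDs or correlations that the protocol does not give.
- A reader might think that the treatment factor hides the dose levels. Section 17.4.4 already pools placebo and asks for a contrast at each dose.

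**Conclusion.** The main point holds as a matter of text. The baseline rule is wrong for HR, PR and QRS, and the carried-over covariate is the wrong one; both conflict with 8.2.1 and 17.4.5. Followed literally, the three categories based on a 25% rise are empty in practice, and the low-HR category counts every value below 50 bpm. This rests on a QTc baseline of about 350 to 450 msec, of which 350 is assumed. No bias in the comparison with placebo is shown from the covariate alone.

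The secondary point holds only as a redundancy. The rank is one short with unstructured (78 of 79) and with compound symmetry (2 of 3), and full with AR(1). The marginal covariance, least-squares means and standard errors are the same for every split. A convergence or Hessian failure unrelated to the data is possible, depending on the software; its frequency is not shown.

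The primary exposure-response model in 17.4.3 names neither an unstructured nor a compound-symmetry matrix, and its response is QTcF. Its decision rule, the sample size and the power are unaffected. The matter should be corrected, but it does not threaten the trial's main conclusion.

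**What to change.** - **17.4.1:** define baseline, for each ECG parameter, as the mean of that same parameter at 45, 30 and 15 min before dosing on Day 1.
- **17.4.4 and the synopsis paragraph:** state that the HR, PR and QRS models use the parameter's own baseline as covariate in place of baseline QTcF.
- **17.4.4 and the synopsis paragraph:** omit the random subject intercept when the matrix is unstructured or compound symmetry, and keep it only with a structure such as AR(1), where it is identifiable.

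The cost is protocol and SAP wording plus programming. The pre-dose measurements are already planned, so no extra data, subjects or time are needed.

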#### 17.4.5 Categorical analyses

The analysis results for categorical outliers, and T-wave morphology will be summarized in frequency tables with counts percentages for both number of subjects and number of time points. For categorical outliers, the number (percentage) of subjects as well as time points who had increases in absolute QTcF values  $>450$  and  $\leq 480$  msec,  $>480$  and  $\leq 500$  msec, and 500 msec, and changes from pre-dose baseline of  $>30$  and  $\leq 60$  msec, and  $>60$  msec; increase in PR from pre-dose baseline  $>25\%$  to a PR  $>200$  msec; increase in QRS from pre-dose baseline  $>25\%$  to a QRS  $>120$  msec; decrease in HR from pre-dose baseline  $>25\%$  to a HR  $<50$  bpm; and increase in HR from pre-dose baseline  $>25\%$  to a HR  $>100$  bpm will be determined. For T-wave morphology, the analyses will be focused on change from baseline (*i.e.*, treatment-emergent changes).

### 17.5 Description of study population

#### 17.5.1 Demographics and baseline characteristics

Descriptive statistics for demographics, weight and height will be presented by treatment.

#### 17.5.2 Medical history and concomitant medication

Medical/surgical history and prior/concomitant medications will be presented by treatment using descriptive statistics and listings.

#### 17.5.3 Treatment compliance

The number of subjects treated in each treatment period and their individual dose will be tabulated.

### 17.6 Analysis of primary endpoints

#### 17.6.1 Electrocardiogram

All ECG data will be listed for each subject and summarized as the vital signs parameters. In addition, ECGs will be categorized as "normal", "abnormal, not clinically significant", or

”abnormal, clinically significant” (as judged by the Investigator) and summarized by treatment and period using frequency tables.

## 17.6.2 Telemetry

Ambulatory ECG telemetry will be used for cardiac surveillance up to 24 hrs after dose administration.

## 17.7 Analysis of secondary endpoints

### 17.7.1 Physical examination

Abnormal findings will be specified and presented by subject and summarized by treatment and period.

### 17.7.2 Vital signs

Vital signs (systolic/diastolic blood pressure and pulse) will be summarized by treatment and period using descriptive statistics.

### 17.7.3 Safety laboratory analyses

Safety laboratory data will be presented by individual time courses for each parameter and subject and summarized by treatment and period.

#### 17.7.4 Adverse Events

All AE data will be fully listed by Investigator terms and MedDRA Preferred Term (PT). AE data will be summarized by System Organ Class (SOC) and PT.

### 17.7.5 Definition and calculation of folate pharmacokinetic parameters

The PK analysis will be based on the PPAS and subcontracted by the Sponsor to PKxpert. The PK parameters will be calculated by non-compartmental pharmacokinetic analysis (NCA) using the software Phoenix WinNonlin® version 6.4 or later (Pharsight Corporation, U.S.A.).

The following non-compartmental PK parameters will be assessed for [6R]-5,10-MTHF, [6S]-5-Methyl-THF, [6S]-THF and [6S]-5-Formyl-THF, if data permit:

**AUC** Area under the plasma concentration-time curve from time 0 to infinity. Calculated using the linear/log trapezoidal rule with extrapolation to infinity.

$$AUC(0 - t_{\max}) = \left( \sum_{i=1}^{n-1} \frac{C(i) + C(i+1)}{2} \cdot (t(i+1) - t(i)) \right)$$

The log trapezoidal rule is used from time  $t_{\max}$  to the last time point  $t$ :

$$AUC(t_{\max} - t) = \left( \sum_{i=1}^{n-1} \frac{C(i) - C(i+1)}{\ln\left(\frac{C(i)}{C(i+1)}\right)} \cdot (t(i+1) - t(i)) \right)$$

Extrapolation to infinity is performed using:

$$AUC(t - \infty) = \frac{C(t)}{\lambda_z}$$

$AUC_{\text{last}}$	Area under the plasma concentration-time curve from time 0 to the last time point $t$ .
$AUC_{\tau}$	Area under the plasma concentration-time curve in a dosing interval. Calculated using the linear/log trapezoidal rule with extrapolation to $\tau$ , if required
$AUC_{\% \text{Extrap}}$	Percentage of $AUC$ that is due to extrapolation from the last concentration to infinity:
	$AUC_{\% \text{Extrap}} = \frac{AUC(t - \infty)}{AUC} \cdot 100\%$
$AUMC$	Area under the first moment curve extrapolated to infinity based on the last observed concentration.
	$AUMC = AUMC_{\text{last}} + \frac{t_{\text{last}} \cdot C_{\text{last}}}{\lambda_z} + \frac{C_{\text{last}}}{\lambda_z^2}$
$C_0$	Back extrapolated concentration at time point 0 after intravenous administration
$C_{\max}$	Maximum plasma concentration
$C_{(\text{time})}$	Plasma concentration at a certain time
$C_{\text{ss}}$	Steady-state drug concentration in plasma
$CL$	Total body clearance for intravenous administration.
	$CL = \frac{\text{Dose}}{AUC}$
$LLOQ$	Lower Limit of Quantification
Mean	Arithmetic mean, otherwise specified
$MRT$	Mean Residence Time extrapolated to infinity.
	$MRT = \frac{AUMC}{AUC}$
$NCA$	Non-Compartmental pharmacokinetic Analysis
$PK$	Pharmacokinetics

Tau ( $\tau$ )	Dosing interval
$t_{\max}$	Time at which maximum plasma concentration is observed.
$t_{1/2}$	$t_{1/2} = \frac{\ln 2}{\lambda_z}$
	Terminal half-life:
$\lambda_z$ ( lambda z )	Terminal rate constant. Calculated by log-linear regression of concentrations versus time
$V_z$	Volume of distribution based on the terminal phase.
	$V_z = \frac{\text{Dose}}{\text{AUC} \cdot \lambda_z}$
$V_{ss}$	Volume of distribution based at steady state.
	$V_{ss} = MRT \cdot CL$

Descriptive statistics for the PK parameters will be presented by treatment group with number of measurements, arithmetic mean, SD, Coefficient of variation (CV), median, minimum, maximum, geometric mean, geometric CV%.

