#### *Pharmacokinetic analysis (Secondary objective)*

The PK analysis will be based on the PPAS and subcontracted by the Sponsor to PKxpert. The PK parameters will be calculated by non-compartmental analysis (NCA) using the software Phoenix WinNonlin® version 6.4 or later (Pharsight Corporation, U.S.A.).

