## 9 INVESTIGATIONAL PLAN

### 9.1 Overall study design and schedule of events

An adaptive randomised, double-blind, single-centre, placebo-controlled Phase I study evaluating ECG effects, safety, tolerability and PK of single ascending doses of Modufolin® for Injection, 100 mg in healthy male volunteers.

Thirty-three (33) eligible and consenting subjects will be included in 3 cohorts, 11 subjects in each cohort. Within each cohort, subjects will be randomised to receive either placebo (3 subjects) or Modufolin® for Injection, 100 mg (8 subjects).

There will be 3 pre-defined ascending dose-levels. Additional dose levels may be considered if recommended by the internal Safety Review Committee (iSRC; see Section 9.1.2). There will be an interval of at least 7 days between each dose level to allow time for safety data to be analyzed and evaluated by the iSRC. The iSRC will have the choice to decide to escalate the dose as planned, reduce or increase the dose escalation step, repeat the dose, reduce the dose or terminate the study.

The total study duration for the subjects will be approximately 5 weeks and there will be in total 3 visits to the clinic. Subjects will be screened for eligibility according to study-specific inclusion/exclusion criteria (see Sections 10.4 and 10.5) within 4 weeks prior to start of study treatment (Visit 1; Screening visit). The subjects will be confined to the research clinic from the evening before dosing (Day -1) until 24 hrs post dose (Days 1 and 2). The subjects should be fasting overnight (8 hrs) before IMP/placebo administration until 4 hrs post-dose. A Follow-up Visit will be performed 5 to 10 days after dose administration of for each cohort.

The timing of all study assessments is shown in the Schedule of events provided in Table 1.

Further details about the randomization procedures are presented in Section 10.8, procedures for maintaining the blind in Section 10.9 and treatment administration in Section 11.6.

Table 1 Schedule of events (2 pages)

Visit number	1												2												3	
	Screening												In-clinic period												FU	
Day	-28 to -1		-1		1												2		6 to 11							
Time points	-		-2 h	-45 min	-30 min	-15 min	0	5 min	15 min	30 min	1 h	2 h	3 h	4 h	5 h	6 h	8 h	12 h	24 h	-						
Time windows (min)	-	-	-	±2	±2	±2		±2	±2	±2	±5	±5	±5	±5	±5	±5	±5	±5	±5	±60	-					
Informed consent	x																									
Demographics	x																									
Medical/surgical history	x																									

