#### 17.3.2 Per Protocol Analysis Set

The Per Protocol Analysis Set will consist of all subjects who have been randomized and completed the study period without any major protocol deviations. All protocol violations will be judged as major or minor at the clean file meeting.

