### 17.3.4 PK Analysis Set

The PK Analysis Set will include all subjects who have evaluable plasma concentration data for Modufolin® and for whom one or more of the designated PK parameters can be determined.

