### 17.3.6 PK/QTc Analysis Set

The PK/QTc Analysis Set will include all subjects who are in both the QT/QTc Analysis Set and PK Analysis Set with at least one pair of post-dose PK and QTcF data from the same time point. The PK/QTc Analysis Set will be used for the exposure-response analysis in the electrocardiogram analysis.

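### The PK analysis is tied to the Per Protocol set although a concentration-based PK Analysis Set is defined, so a usable profile can be lost for reasons unrelated to PK

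*Protocol*

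**What the plan says.** Section 17.7.5 of the protocol fixes the population for the non-compartmental analysis: "The PK analysis will be based on the PPAS and subcontracted by the Sponsor to PKxpert". The synopsis, under the pharmacokinetic analysis for the secondary objective, repeats it: "The PK analysis will be based on the PPAS". PPAS is missing from the abbreviation list, but only the Per Protocol Analysis Set fits it.

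Section 17.3.2 admits to that set randomised subjects who "completed the study period without any major protocol deviations". The grading rule is "All protocol violations will be judged as major or minor at the clean file meeting"; no criterion specific to PK is given.

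Section 17.3.4 defines a different set: "The PK Analysis Set will include all subjects who have evaluable plasma concentration data". The analyte is Modufolin, and the second requirement is that at least one PK parameter is estimable. It sets no condition on completion or deviations. Its only stated use is in section 17.3.6, where the PK/QTc set consists of "all subjects who are in both the QT/QTc Analysis Set and PK Analysis Set", with at least one paired post-dose observation.

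**The concern.** The two sets answer different questions. The PK Analysis Set asks whether a subject's concentrations can be used. The Per Protocol set asks whether the subject finished and followed the whole protocol. For describing PK after one supervised injection, the first question is the relevant one.

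Two things are at stake.

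- **Selection.** With a single dose, any withdrawal for a drug effect comes after dosing, when the early samples may already exist. Section 10.7.1.1 withdraws subjects on QTc criteria, and section 9.1.3 supports stopping participation after a Grade 3 adverse event. Those subjects would not complete, so they would leave the PK summaries. The subject replacement paragraph also excludes from replacement anyone withdrawn for a possibly or probably related event. Whether such subjects have unusual exposure is not known from the document.
- **Consistency with the primary analysis.** Section 17.4.3 predicts the QTc effect at the geometric mean Cmax of each active group. The slope comes from a set built on the PK Analysis Set, while Cmax is a parameter of an analysis restricted to the Per Protocol set.

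**Working it through.** **1. The plan's own figure.** No figure is attached to the choice of PK set, so the nearest one, the power in section 17.2, was checked first. Inputs: SD 7 msec, margin 10, assumed effect 3, 24 active and 9 placebo subjects, 1-sided 0.05.

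- Power = Φ[(10 − 3)/(7·√(1/9 + 1/24)) − 1.645] = Φ(2.558 − 1.645) = 0.820; the noncentral t with 31 df gives 0.804.
- For 48 and 18 subjects: 0.976 (normal) and 0.973 (t).

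These agree with the stated 82% and 97.5% to within two percentage points. The choice of PK set does not enter the calculation.

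**2. The definitions side by side, for an active subject with a usable profile.**

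| Situation | PK Analysis Set | Per Protocol set |
|---|---|---|
| Completes, no major deviation | in | in |
| Withdrawn after dosing | in | out |
| Does not complete the study period | in | out |
| Major deviation unrelated to PK | in | out |

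The third row is realistic because the last in-clinic time point in Table 1 is 24 h, while section 9.1 adds: "A Follow-up Visit will be performed 5 to 10 days after dose administration". Study period is not defined in section 17.3.2. Section 9.1 counts three visits in the total duration and section 15.5 ends the clinical part at the last visit, so including follow-up is the natural reading, but it is not stated.

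**3. Chance that a profile is lost.** The document gives no rate. Assume an independent probability p that an active subject leaves the Per Protocol set, and use 1 − (1 − p)^n.

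| p (assumed) | at least 1 of 8 | at least 1 of 24 |
|---|---|---|
| 2% | 15% | 38% |
| 5% | 34% | 71% |
| 10% | 57% | 92% |

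**4. Precision of a dose-group geometric mean.** The factor is exp[t(0.95, n−1)·s/√n], with s = √ln(1 + CV²). Appendix 18.3 gives 23300 ± 6680 ug/L at 10 min after 500 mg/m² (n=6, patients), so CV ≈ 6680/23300 = 29%. Using this for Cmax in healthy men is an assumption, so a range is shown.

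| CV | n = 8 | n = 7 | n = 6 |
|---|---|---|---|
| 15% | 1.11 | 1.12 | 1.13 |
| 29% | 1.21 | 1.23 | 1.26 |
| 40% | 1.29 | 1.33 | 1.37 |

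On the SD scale, t/√n goes from 0.670 (n = 8) to 0.734 (n = 7), a widening of about 10%.

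**5. Effect on the primary prediction.** At 29% CV, s = 0.284. Removing one of 8 subjects who lies z SDs from the group's log mean shifts that mean by z·s/7: 0.041 for z = 1 and 0.081 for z = 2. The geometric mean Cmax therefore moves by about 4% to 8%. If the whole 3 msec planning effect scales with concentration (assumption), the prediction moves by roughly 0.12 to 0.25 msec against a 10 msec margin.

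**The case against.** The strongest reply is that the protocol makes the same choice in the synopsis and in the body, and nowhere assigns the PK Analysis Set to the non-compartmental analysis. That is correct: the intended use is inferred from the set's name and definition. The inference does not carry the point alone, because the Per Protocol filter is poorly suited to this analysis whatever the other set was meant for.

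Four stronger readings are tempting but not supported.

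- **That profiles will be lost.** Dosing is supervised, subjects stay in the clinic until 24 h, and the clean file meeting can weigh the relevance of a deviation. The number lost may be zero. Optional replacement can restore numbers, though not the lost profile.
- **That the Per Protocol set is wrong because its placebo subjects have no PK data.** Table 1 does not limit sampling to active subjects, four folates are assayed, and section 7.2.2 describes the compound as endogenous. Placebo subjects may have measurable levels, and PK statistics are presented by treatment group, so their presence does no harm.
- **That the confidence interval widening damages a planned PK result.** The list of PK summary statistics in 17.7.5 contains no confidence interval. Only the general rule in 17.1 mentions one, and there is no PK test or precision target. The widening illustrates lost information and no more.
- **That the QTc conclusion is threatened.** Section 17.4.3 refers to subjects in each active group and does not restrict Cmax to the Per Protocol set. The mismatch arises only if the restricted analysis is the source of those values, and step 5 shows that its size is small.

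**Conclusion.** The point holds as an inconsistency of modest size. The protocol bases PK on a filter unrelated to PK, while it defines a concentration-based set and uses that set for the exposure-response analysis. Followed literally, it allows usable active profiles to be dropped, some of them for tolerability, and allows Cmax and slope to rest on different subjects.

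The loss is conditional, and no rate can be taken from the document; the 2% to 10% used above are assumptions. With one subject of 8 lost at an assumed 29% CV, the confidence factor moves from 1.21 to 1.23 and the QTc prediction by at most about a quarter of a millisecond for a subject up to 2 SDs from the mean. Sample size and stated power do not change. The statistical analysis plan was not available, but the protocol does not defer this choice: it states it twice.

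**What to change.** - In section 17.7.5 and the synopsis, replace PPAS with PK Analysis Set, and present the PK parameter summaries by active dose group.
- Leave the definition in section 17.3.4 unchanged. Do not limit the set itself to subjects dosed with Modufolin: the PK/QTc set is an intersection with it, and the primary model compares active with placebo. Any limit to active subjects belongs to the summary tables only.
- State that an individual profile is excluded only for an event or deviation that affects PK, decided before unblinding.
- State that the geometric mean Cmax in section 17.4.3 uses the same individual values as the PK tables.
- Keep the Per Protocol set, if wanted, as a sensitivity analysis.

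The cost is a few sentences in the two places and one in 17.4.3. No new data, assessments or subjects are needed.
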